6.3 SUBJECT SETS ANALYSED

The following patient sets are defined for analysis.

[figure not shown]

Safety Set (SAF)

This patient set includes all patients who received at least one dose of study drug in the overall maintenance period. This set will be the main analysis set used for presentation of efficacy and safety data. This set was formally called the Treated Set in the CTP.

Table 6.3:1 illustrates the data sets that are to be used for each category class of endpoints. For explanation of the different methods of handling missing data, see Section 6.6.

Table 6.3:1 Patient sets analyzed

6.5 POOLING OF CENTRES

All patients from all centers will be pooled for statistical analysis.

6.6 HANDLING OF MISSING DATA AND OUTLIERS

Section 7.3 of the CTP describes the handling of missing data.

Based on the different reasons for patients' data missing, different approaches will be used to assess the impact of missing data on the endpoints of this trial, depending upon the type of the endpoint.

6.6.1 Withdrawals

The reasons for withdrawal from treatment will be reported as indicated on the eCRF.

6.6.2 Efficacy endpoints

Refer to Section 7.3 of the CTP for a description of the handling of missing data for efficacy endpoints.

As described in Section 4, due to limitations in the CRF collection of data, it is not feasible to calculate either of the two secondary efficacy endpoints;

6.6.3 Safety endpoints

For safety data, including the primary endpoint, no missing data imputations are planned.

The only exceptions where imputation might be necessary for safety evaluation are AE dates,

Missing or incomplete AE dates are imputed according to BI standards (see KM Asset BI-KMED-BDS-HTG-0035 (3)).

- o If the day of the end date is missing, then the end date is set to last day of the month (or to the patient's last contact date, if it is earlier than the last day of the month).
- o If the day and month of the end date are missing then the end date is set to 31st of December of the year (or to the patient's last contact date, if it is earlier than the 31st of December of the year).
- o If the day of the start date is missing, the start date is set to the first day of the month.
- o If the day and month of the start date are missing then the start date is set to the 1st of January of the year.

All other cases need to be assessed by the trial team on an individual basis, using the above points as guidance.

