5.2.6.2 Adverse event collection and reporting

5.2.6.2.1 AE Collection

The investigator shall maintain and keep detailed records of all AEs in the patient files. The following must be collected and documented on the appropriate CRF(s) by the investigator (special notes on SAE form reporting where needed):

- From the time of first dose of trial drug administration in the extension trial until the individual patient's end of trial:
all AEs (serious and non-serious) and all AESIs.
- All AEs that started in the parent trial (onset date in parent trial) and are still ongoing after 1st IMP administration in the extension trial:
 - Re-record the AE in the extension trial eCRF with the same information as it was recorded in the parent trial.
 - Should the AE end during the course of the extension trial,
⇒ update both - the extension trial eCRF and the parent trial eCRF. If the parent trial is already locked, update only the extension trial eCRF. In this case the

update for the parent trial will be handled outside of the eCRF of the parent trial.

- However, concerning reporting on the SAE form (if applicable), the follow-up report will still be sent on the parent trial SAE form, no new SAE form is to be completed for the extension trial.
- If the intensity of an ongoing AE changes after 1st IMP administration in the extension trial:
 - ⇒ update both - the extension trial eCRF and the parent trial eCRF- with the end date for the initial/previous intensity. If the parent trial is already locked, update only the extension trial eCRF. In this case the update for the parent trial will be handled outside of the eCRF of the parent trial.
 - ⇒ The AE with the new intensity will be handled as new event; this means it is only recorded in the extension trial eCRF.
 - Example: If the intensity increased then the new AE name/term should contain “Worsening of...” or “Exacerbation of...”

Considerations for reporting on the SAE form, when intensity change qualifies as worsening/exacerbation of an event that had already been reported on the SAE form:

- corresponding follow up report to be sent on the parent trial SAE form with date of worsening as event end date.
- extension trial SAE form to be sent as initial report for the extension trial for new event “Worsening/Exacerbation of....” with date of worsening as onset date.

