Considerations for reporting on the SAE form, when intensity change qualifies as worsening/exacerbation of an event and requires for the first time reporting on the SAE form (meeting for the first time seriousness/AESI criteria):

- only extension trial SAE form to be sent - as initial report for the extension trial for new event “worsening/exacerbation of....” with date of worsening as onset date.

- All AEs with an end date **before** the 1st IMP administration in the extension trial, even if Informed Consent of the extension trial was already signed:
 - Record only in the eCRF of the parent trial.
 - In case of an AE reportable on the SAE form, send the update only on the SAE form of the parent trial.
 - Do not re-record in the extension trial eCRF, do not complete a new SAE form for the extension trial.
- After the EoS visit in the extension trial:

The investigator does not need to actively monitor the patient for new AEs but should

only report any occurrence of cancer (cancer of new histology, exacerbations of existing cancer, if applicable) and trial treatment related SAEs and trial treatment related AESIs of which the investigator may become aware of by any means of communication, e.g. phone call. Those AEs should be reported on the BI SAE form (see [Section 5.2.6.2.2](#)) for the extension trial, but not on the CRF (neither on CRF for extension nor for partent trial).

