7.2.2 Primary endpoint analyses

Refer to [Section 2.1.2](#) for the description of the primary endpoint. The primary analyses will be descriptive in nature. All treated patients will be included in the primary analyses. No hypothesis testing is planned.

Adverse events will be coded using the Medical Dictionary for Drug Regulatory Activities (MedDRA). Standard BI summary tables and listings will be produced. All adverse events with an onset between start of treatment of this trial and end of the residual effect period

(REP), a period of 16 weeks after the last dose of trial medication, will be assigned to the on-treatment period for evaluation.

Adverse events that start before first drug intake and deteriorate under treatment will also be considered as 'treatment-emergent'. For all patients who, due to a fistula relapse received the intensified treatment with spesolimab, safety assessments including adverse events, laboratories, vital signs, etc., which occurred subsequent to such intake will be excluded from presentations according to the planned treatment; these data will, however, be included in summaries where all data after any use of spesolimab are displayed.

Exposure-adjusted adverse event incidence rates will be calculated using the following approach:

The incidence rate (per 100 patient years) of a selected adverse event (also known as the incidence density rate or person-time incidence rate) is defined as the number of patients experiencing the adverse event during the time at risk divided by the total time of patients at risk to contribute an event to the analysis multiplied by 100, where:

$$\text{Time at risk (in subject years)} = ((\text{date of onset of AE} - \text{study drug start date}) + 1) / 365.25$$

The study drug start date refers to the start date of this trial. If, for a patient, no treatment emergent adverse event occurred, then the time at risk will be censored at the minimum of: date of death; drug stop date + 112 days; start date of CD inflammatory flare or fistula relapse treatment with spesolimab; last contact date; or, date of database snapshot if an interim analysis was performed.

For each AE, the incidence rate will therefore be calculated as:

$$\text{Incidence rate} = 100 * \text{number of patients with TEAE} / \text{Total TEAE-specific time at risk.}$$

Exact 95% confidence intervals around the observed AE incidence rate will also be provided.

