8.3.1 Source documents

In accordance with regulatory requirements, the investigator should prepare and maintain adequate and accurate source documents and trial records that include all observations and other data pertinent to the investigation on each trial patient. Source data as well as reported data should follow the "ALCOA principles" and be attributable, legible, contemporaneous, original and accurate. Changes to the data should be traceable (audit trail).

Data reported on the CRF must be consistent with the source data or the discrepancies must be explained.

The current medical history of the patient may not be sufficient to confirm eligibility for the trial and the investigator may need to request previous medical histories and evidence of any diagnostic tests. In this case, the investigator must make at least one documented attempt to retrieve previous medical records. If this fails, a verbal history from the patient, documented in their medical records, would be acceptable.

Copies of source documents will be provided to the Sponsor. Before sending or uploading those copies, the investigator must ensure that all patient identifiers (e.g. patient's name,

initials, address, phone number, social security number) have properly been removed or redacted from any copy of the patients' source documents.

If the patient is not compliant with the protocol, any corrective action e.g. re-training must be documented in the patient file.

For the CRF, data must be derived from source documents, for example:

- Patient identification: gender, year of birth (in accordance with local laws and regulations)
- Patient participation in the trial (substance, trial number, patient number, date patient was informed)
- Dates of patient's visits, including dispensing of trial medication
- Medical history (including trial indication and concomitant diseases, if applicable)
- Medication history
- Adverse events and outcome events (onset date (mandatory), and end date (if available))
- Serious adverse events (onset date (mandatory), and end date (if available))
- Concomitant therapy (start date, changes)
- Originals or copies of laboratory results and other imaging or testing results, with proper documented medical evaluation (in validated electronic format, if available)
- Completion of patient's participation in the trial" (end date; in case of premature discontinuation document the reason for it).

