6. GENERAL ANALYSIS DEFINITIONS

6.1 TREATMENT(S)

For basic study information on treatments to be administered, assignment of treatment groups, and selection of doses, refer to CTP Section 4.

Patients who experience a fistula relapse during the maintenance treatment (as defined in CTP Table 2.1: 1) will be administered a single intravenous dose of spesolimab 1200 mg followed by an intensified subcutaneous maintenance dosing schedule with 600 mg q4w.

The following study periods are defined:

Table 6.1: 1 Flow chart of analysis periods which apply to all patients.

Analysis period	On-/off- treatmen t	Start (included)	End (included)
Screening period (Approx 1-2wks)	Off- treatment	Earliest of (Date of informed consent, first screening procedure)	Date/time of injection of first s.c. maintenance study drug minus 1 minute.
Overall maintenance period ¹ (Approx 336 wks)	On- treatment	Date/time of first s.c. maintenance study drug.	Date of last administered spesolimab (irrespective of formulation) + 112 days at 11:59pm.
Follow-up period ²	Off- treatment	Date of last study drug administration (irrespective of formulation) + 113 days at 12:00 AM.	Latest of: i) Date of EOS visit (Week 352 visit); ii) last contact date on End of Study page at 11:59 p m.

Dates are defined individually per patient. If more than one date is associated with a specific visit, measurements associated with a specific date are assigned to a study analysis phase according to the rules specified in the table. An analysis phase will not extend beyond the start date of the following phase.

The on-treatment period is defined as the overall maintenance period (including REP).

For all analysis periods, assessments done on the same day as the first maintenance treatment dose will be assigned to the appropriate analysis phase based on the assessment of date/time. If time is not collected for an assessment, then assignment will be to the previous analysis phase, e.g., to the screening phase.

Treatment Labels

Treatments will be labelled as follows:

"Overall Speso"

¹ The overall maintenance treatment period applies to all patients taking at least one dose of maintenance treatment regardless of flare occurrence. This period will be considered to understand long-term efficacy and safety of spesolimab.

² The follow-up period only exists if the trial completion date is after the date of end of last injection/infusion plus REP.

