7.8.1 Adverse events

AEs will be coded with the most recent version of MedDRA.

The analysis of AEs will be descriptive in nature. All analyses of AEs will be based on the number of patients with AEs and not on the number of AEs. System organ classes (if applicable) will be sorted according to the standard sort order specified by the EMA. Preferred terms (if applicable) will be sorted by total frequency (within system organ class).

For further details on summarization of AE data, please refer to "Analysis and Presentation of Adverse Event Data from Clinical Trials" (4) [KM Asset BI-KMED-BDS-HTG-0041] and "Handling of missing and incomplete AE dates" (3) [KM Asset BI-KMED-BDS-HTG-0035].

The analysis of AEs will be based on the concept of treatment emergent AEs. This means that all AEs will be assigned to either the screening period, the applicable on-treatment period, or the off-treatment period (i.e. follow-up) as defined in Section 6.1. Since only the start date of an AE is collected (without start time), any AE which occurs on the same day as the first maintenance treatment will be assigned to the respective on-treatment period.

Refer to CTP Section 7.2.2 for a description of the calculation of exposure-adjusted adverse event incidence rates (per the primary endpoint).

The AE summaries described below will be produced for the following treatment periods:

• The overall maintenance period [based on the SAF]

An overall summary of AEs will be presented. This overall summary will include the class of AESIs. Refer to CTP Section 5.2.6.1.4 for a description of what is considered as an AESI.

The investigator identified AESI will be captured from the eCRF and reported in the "Investigator reported AESI" table. In addition, user defined adverse event categories (UDAEC) identified through specific search criteria will be reported separately; the UDAEC applicable to this trial are stored centrally and will be referenced for this presentation.

Adverse Events classified as 'other significant' will be reported using an adaptation of the ICH E3 (6) and will include those non-serious and non-significant AEs which were reported with 'action taken = drug withdrawn' or 'action taken = reduced'.

Table 7.8.1: 1 Project MEDDRA search criteria for User Defined Adverse Events Categories (UDAEC)

User-defined AE category			
Label	Description		
Infections ALL	Combined search strategy based on the individual UDAECs for infections described below		

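### Partial AE start dates are imputed backwards with no floor at first dose, so a new on-treatment AE can be counted as screening and drop out of the primary TEAE rate

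*SAP*

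**What the plan says.** SAP section 6.6.3 imputes no safety data except AE dates. For start dates it gives two rules: "If the day of the start date is missing, the start date is set to the first day of the month", and "If the day and month of the start date are missing then the start date is set to the 1st of January of the year". The matching end-date rules are capped at the patient's last contact date, but the start-date rules have no bound. The section cites an internal standard on incomplete AE dates. It leaves to individual assessment by the trial team only the cases that the listed rules do not cover.

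Five other places decide what an imputed start date does:

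- SAP Table 6.1:1 ends the screening period at "Date/time of injection of first s.c. maintenance study drug minus 1 minute"; the on-treatment period begins with that injection.
- SAP section 7.8.1 assigns each AE to screening, on-treatment or follow-up. Because no onset time is collected, "any AE which occurs on the same day as the first maintenance treatment will be assigned to the respective on-treatment period".
- Protocol section 7.2.2 counts an AE that began before first intake as treatment-emergent only if it worsens under treatment. On the origin of time at risk it says "The study drug start date refers to the start date of this trial".
- Protocol section 5.2.6.2.1 collects all AEs "From the time of first dose of trial drug administration in the extension trial". Parent-trial AEs still ongoing after that dose are re-recorded. For AEs that ended before it, the instruction is "Do not re-record in the extension trial eCRF".
- Protocol section 8.3.1 lists among source data "Adverse events and outcome events (onset date (mandatory), and end date (if available").

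**The concern.** The imputation can move an AE to the wrong side of first dose, and always in the same direction. The only AEs exposed are early on-treatment ones, and the only possible error is to date them before treatment. The same-day rule in SAP section 7.8.1 does not help, because it applies only when the AE date equals the first-dose date.

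The result also contradicts the reason the record exists. The extension eCRF holds AEs from first dose onward plus re-recorded ongoing parent-trial AEs. Any AE in it that was not carried over must have begun on or after first dose, so a screening date for it is wrong by construction.

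The primary endpoint is the exposure-adjusted rate of patients with a TEAE, and each patient contributes through the first TEAE. With at most 20 patients (protocol section 7.5), one misplaced record can show in the overall rate. It shows more readily in a system organ class or preferred-term row, or in the separate tables for SAEs, AESIs and user-defined categories.

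**Working it through.** The plan gives no figure of its own on this point. The check applies the written rules to dates and then to an assumed data set.

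**1. The rules on one patient (assumed dates).** First dose 15 March 2021; true onset of a new AE 24 March 2021.

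| Known part of start date | Imputed start | Period assigned | (onset − first dose) + 1 |
|---|---|---|---|
| Month and year | 1 March | Screening | −13 days |
| Year only | 1 January | Screening | −72 days |

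The last column is the numerator of the time-at-risk formula in protocol section 7.2.2. It would apply only if the AE were kept as a TEAE despite its imputed date.

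**2. How general this is.** Over the 365 possible first-dose dates in a non-leap year:

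- A new AE in the first-dose month with the day missing goes to screening for 353 dates (96.7%), all but the 1st of each month.
- A new AE in the first-dose year with day and month missing goes to screening for 364 dates (99.7%).
- If such an AE were kept as a TEAE, time at risk would run from 0 (first dose on the 2nd) to −29 days (on the 31st) with the day missing, and down to −363 days (31 December) with day and month missing.

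**3. The exposed window.** For day-missing AEs the window runs from first dose to the end of that month, or is zero if dosing starts on the 1st. Averaged over 365 start dates it is 14.7 days. As a share of assumed on-treatment time:

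- 14.7/112 = 13.1%
- 14.7/448 = 3.3%
- 14.7/1120 = 1.3%

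**4. Effect on the any-TEAE rate (all inputs assumed).** N = 20. Fourteen patients have a first TEAE at day 60, one at day 10, and five are censored at day 448. The day-10 AE is the one with the partial date. Rate = 100 × patients with a TEAE / (days at risk / 365.25).

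| Scenario | Days at risk | TEAE patients | Rate per 100 PY | Change |
|---|---|---|---|---|
| True dates | 14×60 + 10 + 5×448 = 3090 | 15 | 177.3 (exact 95% CI 99.2 to 292.4) | – |
| AE lost, patient's only TEAE | 14×60 + 6×448 = 3528 | 14 | 144.9 | −18.3% |
| AE lost, later TEAE at day 60 | 15×60 + 5×448 = 3140 | 15 | 174.5 | −1.6% |
| AE kept with −13 days | 14×60 − 13 + 5×448 = 3067 | 15 | 178.6 | +0.7% |
| AE floored at first dose (1 day) | 14×60 + 1 + 5×448 = 3081 | 15 | 177.8 | +0.3% |

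**5. Sensitivity to the assumptions.** Inputs varied: 15 or 18 TEAE patients, other first TEAEs (and the later one) at day 60 or 120, censoring at day 448 or 1,120.

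- Only TEAE lost: −16% to about −30% (largest −29.5%).
- Later TEAE exists: −0.8% to −3.6%.
- Kept with −13 days: +0.3% to +1.2%.

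**6. A single preferred term (assumed).** Twenty patients, three with the term at day 10, the other 17 followed for one year: 3/(17 + 30/365.25) gives 17.6 per 100 PY (95% CI 3.6 to 51.3). Losing one of the three gives 2/(18 + 20/365.25), or 11.1 (1.3 to 40.0).

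**The case against.** The strongest objection is that the operative algorithm may sit in the internal standard that SAP sections 6.6.3 and 7.8.1 both cite. That standard is not available here and may contain a first-dose floor. This stands as a limit on what can be claimed. But the SAP spells out its own rules, down to the cap on end dates, and a programmer following them gets the wrong period.

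The second objection is rarity. Onset date is mandatory in source data, and visits are every four weeks, with the second dosing visit at Day 29 ±7. Recall for first-month AEs is therefore short, and year-only onset dates are hard to envisage. The large effect also needs the misdated AE to be the patient's only TEAE over the whole follow-up. All of this stands. The extreme values of −29 and −363 days require onset on the dosing day itself and apply only if the AE is kept against its imputed date, so they mark the limits of the formula and are not expected results. The 13.1% share describes roughly a single-dose patient; 3.3% or 1.3% suits longer treatment.

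Third, the trial is single-arm and descriptive, was stopped early and will have an abbreviated report. Individual AE listings would let a careful reader spot a new AE dated before first dose. That limits the harm, but a listing does not correct the summary rate, and the provision for individual assessment does not reach cases that the listed rules already resolve.

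**Conclusion.** The point holds for the text as written. Applied literally, SAP section 6.6.3 puts a new on-treatment AE into screening whenever its start date is partial, its known part matches the month or year of first dose, and first dose was not on the first day of that month or year. The AE is then treatment-emergent only if it later worsens.

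The size is conditional. The documents do not say how many partial dates there are, and there may be none. If one occurs, the any-TEAE rate falls by about 1% to 4% when the patient has a later TEAE, and by about 16% to 30% when the AE was the only one, over the assumed inputs above. Even the sole-TEAE result of 144.9 lies well inside the interval around 177.3. This is therefore a small correction to the primary safety analysis that should be made, and it does not threaten the trial's conclusions. Confidence is medium because the cited standard could not be read.

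**What to change.** Add to SAP section 6.6.3:

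> If the known part of an AE start date is compatible with onset on or after first dose in this trial, and the AE is not re-recorded from the parent trial, the imputed start date is the later of the first day of that month (or year) and the date of first dose, but not later than the AE end date.

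Under SAP section 7.8.1 an AE imputed to the first-dose date is on-treatment, with one day at risk. Limiting the floor to AEs that were not carried over keeps genuine pre-dose events from being relabelled. If the cited internal standard already has this floor, repeat it in the SAP.

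The cost is one sentence and one derivation condition. First-dose dates and parent-trial AE records are already held, and with at most 20 patients the affected records can be checked by hand before database lock.
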